**FRED HUTCHINSON CANCER RESEARCH CENTER
UNIVERSITY OF WASHINGTON SCHOOL OF MEDICINE**

Current version: 3

Previous version:2

**Management of Venous Thromboembolic Events (VTE) in Patients
with Hematologic Disorders and Treatment-Induced
Thrombocytopenia: a Pilot Study**

Principal Investigator:

- [name], Professor, UW [contact])

Co-Investigators at FHCRC/UW

- [name] PhD, Assistant Member, FHCRC, Professor, UW [contact])
- [name], Professor, UW [contact])

Study Coordinator FHCRC:

- [name], Clinical Research Coordinator SCCA [contact]);
email:[contact]

Data Coordinator FHCRC:

- [name], Clinical Research Coordinator,, SCCA [contact]); email:
[contact]

Emergency Phone (24 hours):

For non-transplant patients: Call the paging operator at the University of Washington Medical Center at [contact], and ask for the Fellow on call for Hematology/Oncology.

For transplant patients: Call the 8NE front desk at the University of Washington Medical Center at [contact], and ask for the triaging provider covering the transplant service.

PROTOCOL SYNOPSIS

Protocol Title	Management of Venous Thromboembolic Events (VTE) in Patients with Hematologic Disorders and Treatment-Induced Thrombocytopenia: a Pilot Study
Protocol Number	
Protocol Sponsor	None
Trial Phase	Pilot
Trial Type	Noninferiority
Clinical Indication	Management of treatment-induced thrombocytopenia during anticoagulation
Study Objectives	
 1) Determine feasibility of an RCT comparing platelet transfusion thresholds of 30×10^9 vs 50×10^9 in anticoagulated patients 2) Report bleeding outcomes as they would be in a full trial 3) Report patient reported outcomes as they would be in a full trial
Study Design	Randomized controlled trial
Population	Adult patients with moderate to severe thrombocytopenia related to the treatment of a hematologic malignancy and/or stem cell transplant for a hematologic disorder who require anticoagulation for a recently diagnosed venous thrombosis.
Primary Endpoints	(1) Feasibility defined as ≥ 12 patients enrolled over a 1-year period and (2) $\geq 70\%$ compliance with study-determined transfusion threshold at the time of count recovery
Secondary Endpoints	
 (1) Number of eligible patients over a 1-year period (2) Percentage of eligible patients providing consent (3) Progressive or new venous or arterial thrombosis (4) Bleeding events by WHO grade (5) Platelet transfusions (6) PRBC transfusions (7) Transfusion related outcomes (8) Quality of life (FACT-Th18)
Type of control	Institutional standard of care
Trial Blinding	Unblinded
Treatment Groups	A: transfusion threshold of $30 \times 10^9/L$ B: transfusion threshold of $50 \times 10^9/L$
Treatment Schedule	Transfusions will be administered as needed (based upon randomized threshold) throughout a single period of treatment-related thrombocytopenia OR 30 days, whichever is shorter
Number of trial subjects	12
Estimated duration of trial	One year
Duration of Participation	≤ 63 days

ABBREVIATIONS

CT scan	Computed tomography scan
ATE	Arterial thromboembolism
HSCT	Hematopoietic Stem Cell Transplant
SCCA	Seattle Cancer Care Alliance
VTE	Venous thromboembolism
AML	Acute myeloid leukemia
ALL	Acute lymphocytic leukemia
CML	Chronic myeloid leukemia
CLL	Chronic lymphocytic leukemia
MDS	Myelodysplastic syndrome
WHO	World Health Organization
DIC	Disseminated intravascular coagulation
PT	Prothrombin time
PTT	Partial thromboplastin time
V/Q	Ventilation/perfusion scan
APL	Acute promyelocytic leukemia
HLA	Human leukocyte antigen

Contents

1.0 GENERAL INFORMATION	7
1.1 Protocol Title	7
1.2 Sponsor Information	7
1.3 Investigator Information	7
2.0 INTRODUCTION TO THE PROTOCOL	7
2.1 Background and Rationale	7
2.2 Clinical Data to Date	8
2.3 Transfusion Threshold Rationale	9
2.4 Risks/Benefits	9
3.0 OVERVIEW OF CLINICAL TRIAL	10
3.1 Study Objectives	10
3.1.1 Primary Objective	10
3.1.2 Secondary Objectives	10
3.2 Study Population	10
3.3 Study Design	10
3.3.1 Primary Endpoint	10
3.3.2 Secondary Endpoints	11
3.4 Estimated Accrual	11
3.5 Funding Source	11
4.0 SAFETY CONSIDERATIONS	11
4.1 Stopping Rules	11
5.0 SUBJECT ELIGIBILITY	11
5.1 Inclusion Criteria	11
5.2 Exclusion Criteria	12
6.0 Subject Registration	12
7.0 Treatment Plan	13
7.1 Treatment Plan Overview	13
7.2 Baseline/Pre-Treatment Assessment	13
7.3 Randomization	13
7.4 Administration of Transfusions	13
7.5 Concomitant Medication and Supportive Care Guidelines	14
7.5.1 Unfractionated heparin (UFH)	14

7.5.2 Low molecular weight heparin (LMWH)	14
7.5.3 Anticoagulation Dosing Modifications	14
7.6 Transfusion Delays/Modifications	14
7.7 Duration of Therapy	15

1.0 GENERAL INFORMATION

1.1 Protocol Title

“Management of Venous Thromboembolic Events (VTE) in Patients with Hematologic Disorders and Treatment-Induced Thrombocytopenia: a Pilot Study.”

1.2 Sponsor Information

This is a pilot study and will not be sponsored.

2.0 INTRODUCTION TO THE PROTOCOL

This document provides in depth background information and serves as a guidance document for the proper identification, treatment and maintenance of trial patients. This study will be conducted in compliance with the IRB approved protocol, associated Federal regulations and all applicable IRB requirements. The purpose of this study is to evaluate the feasibility of a randomized, controlled trial comparing a platelet transfusion threshold of $30 \times 10^9/L$ to $50 \times 10^9/L$ in anticoagulated patients with treatment related thrombocytopenia. To date no clinical trial has ever investigated the safety and efficacy of any transfusion strategy in this setting. This will be a pilot study in which approximately 12 patients will be enrolled and randomized to one of the two potential transfusion thresholds. Patients will be followed clinically for bleeding, thrombotic and transfusion related outcomes.

2.1 Background and Rationale

Venous thromboembolic disease (VTE) is a common complication of hematologic malignancy. The prolonged periods of thrombocytopenia experienced by these patients during curative-intent chemotherapy and/or hematopoietic stem cell transplant (HSCT) do not appear to provide protection against VTE: the rate of symptomatic VTE may be as high as 5% by day 180 post HSCT.¹ Data to guide management of thrombosis in these patients, particularly during periods of moderate to severe thrombocytopenia, are sparse.

The International Society on Thrombosis and Haemostasis (ISTH) has suggested an empirical cut-off of $50 \times 10^9/L$ as the minimum platelet threshold above which therapeutic anticoagulation is considered to be safe. Accordingly, a recommendation has been made to consider platelet

transfusion support to maintain a platelet count above this threshold if therapeutic anticoagulation is warranted, as in the setting of acute VTE.² These recommendations, however, have been made on the basis of expert consensus, as there is no high-quality evidence.

The only data currently available in the literature comes from very small retrospective studies and case series. These suggest the risk of bleeding (WHO grade 2 or greater) among patients with moderate to severe thrombocytopenia is relatively low (between 7.7 and 9.4% over a 3-6 month period) when patients are initiated on anticoagulation and then transfused toward a goal of $40\text{-}50 \times 10^9/\text{L}$.^{3,4} Approximately half of these bleeding episodes represent major bleeding (3.8% of patients).⁴

2.2 Clinical Data to Date

A recent survey of malignant/nonmalignant hematologists and transfusion medicine experts about this topic found a marked degree of variation in proposed transfusion thresholds (ranging from 25 to $50 \times 10^9/\text{L}$).⁵ A recent retrospective study of eighty-two SCCA patients with VTE during a period of treatment-related thrombocytopenia demonstrated that most providers here manage VTE with therapeutic anticoagulation, adjusting the platelet transfusion goal to $50 \times 10^9/\text{L}$, often resulting in two or more weeks of frequent platelet transfusions, potentially repeated in future treatment cycles. Bleeding rates (WHO grade 2 or above) were noted to be somewhat higher than those previously reported in the literature (37% at 30 days), but comparable to or less than rates expected in patients with severe treatment related thrombocytopenia (transfusion threshold $10 \times 10^9/\text{L}$), which is as high as 70% over a period of 30 days or less.⁶ While retrospective assessments of bleeding, particularly grade 2 bleeds, are limited and some bleeds are likely missed by this method, we expect this rate of bleeding is more representative of actual outcomes than those previously reported in the literature.

Our retrospective review demonstrated that the vast majority of patients at our institution in this situation are transfused to maintain a platelet count $\geq 50 \times 10^9/\text{L}$, with the above noted bleeding rate. The majority of bleeds occurred during a time when the platelet count was at or above this goal (mean $52 \times 10^9/\text{L}$) although the retrospective nature made it impossible to define or compare 'at risk' times. We did, however, note a number of transfusion related complications with this strategy including transfusion reactions in 13% of patients and volume overload requiring diuretic therapy or dialysis in 37% of patients.

Patients received a median of 6 transfusions over the 30 days following diagnosis, accompanied by both a financial cost and a drain on resources. While cost data were not collected as a part of this study, previous studies have demonstrated increased cost (as high as \$5700/patient in 2014) associated with the use of prophylactic platelet transfusions to target a platelet count of $10 \times 10^9/\text{L}$.⁷ The higher target of $50 \times 10^9/\text{L}$ utilized for most patients in our retrospective study would naturally cost considerably more, in terms of financial cost to the patients, infusion room time and transportation costs (outpatients), prolongation of hospital stays (inpatients) and burden on the finite resource of blood products.

Another relevant issue is that of platelet refractoriness, defined as repeated, inadequate response to platelet transfusions. Rates of platelet refractoriness may be as high as 21.6%

among inpatients requiring platelet transfusions, adding both to the complexity of caring for such patients, particularly if and when bleeding does occur, and to those additional costs mentioned above including monetary (increased mean hospitalization cost of \$66,000 in the year 2000) and resource utilization (17.8 additional units of platelets/patients).⁸

Furthermore, platelet refractoriness may be a sign of the bigger issue of alloimmunization (defined as platelet refractoriness due to antibodies against antigens found in >25% of platelet donors), a major issue among patients undergoing repeated cycles of chemotherapy or stem cell transplant, requiring long term platelet support. Alloimmunized patients require HLA-matched platelet units from matched/directed donors, adding further to the expense and stress on resources. This is a common problem, affecting approximately five patients on the combined leukemia and transplant services at any given time.

2.3 Transfusion Threshold Rationale

As indicated above, we have demonstrated medical, financial and resource costs with the current institutional approach of transfusing to a threshold of $50 \times 10^9/L$. We hypothesize that a decreased threshold will lead to decreased rates of transfusion-related complications, decreased burden on patients who require frequent transfusions in the inpatient and outpatient setting and decreased financial and resource burden. The rationale behind the experimental threshold of $30 \times 10^9/L$ arises from expert consensus, including experts in transfusion medicine and anticoagulation at our own institution and is being used in clinical practice at a number of other centers across North America with various anticoagulation strategies.⁹ Furthermore, this lower threshold is the most often used in our own institution for patients who are unable to maintain platelet counts $>50 \times 10^9/L$.

2.4 Risks/Benefits

The primary risk of a decreased platelet transfusion threshold would be that of increased bleeding rates. Platelet-type, or bleeding due to defects of primary hemostasis, tends to be primarily mucocutaneous, including epistaxis, gum bleeding and menorrhagia,¹⁰ rather than into soft tissue, joints or body cavities as with disorders of secondary hemostasis (clotting factor deficiencies, including those induced by anticoagulation). Thrombocytopenic bleeding in the unanticoagulated population is largely low grade (WHO grade 2 or less) and rarely requires intervention beyond platelet transfusion.^{6,11}

Potential benefits of a decreased platelet transfusion threshold are numerous. Objective benefits to the individual patient might include decreased rates of transfusion-related complications, including transfusion reactions, infections, volume overload and alloimmunization. Subjective benefits of decreased transfusion frequency/requirement might include improved sense of well-being and quality of life, particularly for outpatients who may require fewer trips for medical care and benefit from increased time at home. Systemic benefits might include decreased overall cost of care and decreased drain on resources, of particular importance when blood products are in short supply.

3.0 OVERVIEW OF CLINICAL TRIAL

3.1 Study Objectives

3.1.1 Primary Objective

1. To determine feasibility of a randomized controlled trial comparing two different platelet transfusion thresholds ($50 \times 10^9/L$ vs $30 \times 10^9/L$) in patients with treatment or malignancy-induced thrombocytopenia requiring therapeutic anticoagulation.

3.1.2 Secondary Objectives

1. To report outcomes as they would be in a definitive study including:
 - a. Progressive or new VTE
 - b. Progressive or new ATE
 - c. Hemorrhagic events (WHO grade 2 or greater)
 - d. A composite of a, b and c.
 - e. Major bleeds (WHO grade 3 or 4)
 - f. Number of platelet transfusions per patient during the study period
 - g. Platelet transfusion related complications (including transfusion reactions, alloimmunization and volume overload)
 - h. Degree to which platelet target thresholds are achieved

3.2 Study Population

The study population will include patients undergoing therapy for hematologic malignancy, including HSCT and/or curative-intent chemotherapy in the setting of acute leukemia at the Seattle Cancer Care Alliance/University of Washington Medical Center. All patients must be experiencing treatment-related thrombocytopenia during a time period for which their treating physician has determined anticoagulant therapy for VTE is necessary and appropriate.

3.3 Study Design

This will be a feasibility/pilot study designed to assess the feasibility of a randomized, controlled trial, comparing a lower platelet transfusion threshold ($30 \times 10^9/L$) to a higher platelet threshold ($50 \times 10^9/L$) in patients who require anticoagulation for VTE in the setting of treatment-induced (either chemotherapy or HSCT) thrombocytopenia for hematologic disease.

We are targeting an enrollment of approximately 1 patient per month. Patients will be enrolled and randomized in a consecutive fashion to minimize selection bias. Blinding will not be feasible in this study.

3.3.1 Primary Endpoint

The primary endpoint of this study will be feasibility of an RCT comparing a lower platelet transfusion threshold ($30 \times 10^9/L$) to a higher platelet threshold ($50 \times 10^9/L$) in patients who require anticoagulation for VTE. To assess feasibility of a multicenter RCT we will evaluate:

1. Number of patients eligible, reasons for ineligibility
2. Number of eligible patients approached for the study

3. Number of patients consenting to enrollment
4. Number of patients successfully following protocol (defined as receiving transfusions 'on protocol' at the end of the study period)

This data will then assist in determining the number of centers likely to be required to appropriately power a definitive study within 2-3 years.

3.3.2 Secondary Endpoints

1. Progressive or new VTE
2. Progressive or new ATE
3. Hemorrhagic events (WHO grade 2 or greater)
4. A composite of a, b and c.
5. Major bleeds (WHO grade 3 or 4)
6. Number of platelet transfusions per patient during the study period
7. Platelet transfusion related complications
 - a. transfusion reactions
 - b. alloimmunization
 - c. volume overload
8. Percent of days on which subjects are transfused (or transfusions are not given) in compliance with the threshold to which they were randomized

3.4 Estimated Accrual

We estimate an accrual rate of approximately one patient per month over a 12-month period. Based upon historical data we estimate approximately 25-30 patients per year will be eligible and are estimating a 45% rate of consent.

3.5 Funding Source

This study will be unfunded, but the PI receives salary source from a T32 grant funded by the National Institute of Health (T32HL007093).

4.0 SAFETY CONSIDERATIONS

4.1 Stopping Rules

The study will be stopped early if major bleeding (WHO grade 3 or greater) is noted in 3 or more patients on the experimental arm once eight patients have been enrolled (and at least four randomized to the experimental arm).

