7.1 Treatment Plan Overview

In this pilot study, patients meeting the inclusion/exclusion criteria and their primary hematologists are asked whether or not they would agree to participate in the randomized treatment assignment (Appendix 1). Patients agreeable to randomization will be assigned in a 1:1 ratio to a higher ($50 \times 10^9/L$) or lower ($30 \times 10^9/L$) platelet transfusion threshold. For those who wish not to be randomized the reason to decline randomization will be recorded, and patients will be managed according to the discretion of their primary hematologist.

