7.7.1 Breaking Randomization

Randomization may be broken and the patient taken off protocol for any of the following reasons. In all cases the new threshold will be noted and the patient will be observed for primary and secondary outcomes until the completion of the study period.

Randomization will be immediately broken and transfusions managed according to the subject's managing provider(s) for any grade 3 or 4 bleeding event. The new threshold will be noted and the patient will be followed for outcomes until the end of the study period. If a grade 3 event completely resolves in <72 hours, is non-life-threatening, does not require permanent discontinuation of anticoagulation and is not reasonably expected to recur (eg vaginal bleeding resolved with hormonal therapy, bleeding from a wound which has been closed), the patient and primary provider may elect to continue with the randomized threshold.

For subjects in whom discontinuation of anticoagulation is deemed necessary by managing providers, randomization will be broken, and a new transfusion threshold will be determined at the discretion of the managing team.

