11.0 Data and Safety Monitoring Plan

Institutional support of trial monitoring will be in accordance with the Fred Hutch/University of Washington Cancer Consortium Institutional Data and Safety Monitoring Plan. Under the provisions of this plan, Fred Hutch Clinical Research Support (CRS) coordinates data and compliance monitoring conducted by consultants, contract research organizations, or Fred Hutch employees unaffiliated with the conduct of the study. Independent monitoring visits occur at specified intervals determined by the assessed risk level of the study and the findings of previous visits per the institutional DSMP.

In addition, protocols are reviewed at least annually and as needed by the Consortium Data and Safety Monitoring Committee (DSMC), Fred Hutch Scientific Review Committee (SRC) and the Fred Hutch /University of Washington Cancer Consortium Institutional Review Board (IRB). The review committees evaluate accrual, adverse events, stopping rules, and adherence to the applicable data and safety monitoring plan for studies actively enrolling or treating subjects. The IRB reviews the study progress and safety information to assess continued acceptability of the risk-benefit ratio for human subjects. Approval of committees as applicable is necessary to continue the study.

The trial will comply with the standard guidelines set forth by these regulatory committees and other institutional, state and federal guidelines.

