16.0 Stopping the Study

[figure not shown]
The investigators may decide to stop the study at any point, for any reason. The following reasons will lead to premature termination of the trial

- WHO grade 3/4 bleeding rate <30% in the lower transfusion threshold arm following enrollment of 8 patients

References

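### The Section 4.1 bleeding rule counts events cumulatively, so its eight-patient precondition prevents almost no false stops and only delays a stop already earned

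*Combined protocol and SAP*

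**What the plan says.** Section 4.1 gives the trial-level bleeding rule. The study stops early if "major bleeding (WHO grade 3 or greater) is noted in 3 or more patients on the experimental arm", and this applies "once eight patients have been enrolled (and at least four randomized to the experimental arm"). The trigger is a number of patients, not a rate, and bleeds before the eighth enrolment are not excluded from it.

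Section 16.0 has a second stopping statement. It begins "The investigators may decide to stop the study at any point, for any reason", then lists one reason for mandatory termination: "WHO grade 3/4 bleeding rate <30% in the lower transfusion threshold arm following enrollment of 8 patients". This also waits for eight patients. It uses a rate, and the printed inequality runs opposite to Section 4.1.

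Three other provisions matter. Section 11.0 says "protocols are reviewed at least annually and as needed by the Consortium Data and Safety Monitoring Committee". Section 7.7.1 acts on the individual after a grade 3 or 4 bleed: "Randomization will be immediately broken and transfusions managed according to" the managing provider, with an exception for some resolved grade 3 events. On pace and allocation, Section 3.4 expects an "accrual rate of approximately one patient per month" for 12 months, and Section 7.1 says that patients "will be assigned in a 1:1 ratio". Neither Section 7 nor Section 13 describes blocking.

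**The concern.** A lead-in is useful for a rate boundary, where one bleed in two patients reads as 50% and says little. Section 4.1 uses a cumulative count. Three bleeds among the first three or four experimental patients will still be three bleeds at patient 8, so waiting cannot cancel a stop. It can only postpone it.

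The rule is also silent where the evidence is strongest. If the true rate were 10%, three or more bleeds would have probability 0.1% in three patients, 0.4% in four and 1.6% in six.

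Section 2.4 names increased bleeding as the main risk of the lower threshold. At stake is how many further patients may be randomised after the protocol's own harm criterion has been met in substance.

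**Working it through.** The documents state no false-stop or detection probability for this rule, so there is no figure to reproduce.

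**Inputs from the documents.** Trigger: 3 experimental-arm patients. Preconditions: 8 enrolled and 4 experimental (Section 4.1). Total: about 12 (Section 2.0). Allocation: 1:1 (Sections 7.1 and 13.1). Accrual: about one per month, from 25–30 eligible per year at 45% consent (Section 3.4). Major-bleed rate: 3.8% in cited literature at a transfusion goal of 40–50 × 10⁹/L (Section 2.1).

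**Assumptions.** The documents give no major-bleed rate for the lower threshold, so *p* is varied from 3.8% to 50%. Allocation is taken as simple 1:1, and bleeds are treated as known at enrolment.

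**Timing.** 25 × 0.45 = 11.25 and 30 × 0.45 = 13.5 patients per year. The eighth enrolment then falls at 8/13.5 × 12 = 7.1 months to 8/11.25 × 12 = 8.5 months, or month 8 at one per month.

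**Chance of stopping.** Each enrolled patient is an experimental-arm bleeder with probability *p*/2.
- Without preconditions: P(Bin(12, *p*/2) ≥ 3).
- As written: the two differ only when exactly three of the 12 patients are experimental and all three bleed, which has probability C(12,3)/2¹² × *p*³ = 0.0537*p*³. At *p* = 50% this is 0.0537 × 0.125 = 0.67 points, so 60.93% − 0.67% = 60.26%.

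**Chance of three experimental bleeds before the eighth enrolment:** P(Bin(7, *p*/2) ≥ 3).

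**Extra patients.** Let *t* < 8 be the enrolment number of the third bleeder, and *g* the first enrolment number of at least 8 with at least four experimental patients (12 if never reached). The mean of *g* − *t* was enumerated exactly.

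| Assumed *p* | Stop, no preconditions | Stop, as written | Three bleeds before 8th enrolment | Mean extra enrolled (experimental) |
|---|---|---|---|---|
| 3.8% | 0.13% | 0.13% | 0.02% | 2.1 (1.0) |
| 10% | 1.96% | 1.95% | 0.4% | 2.1 (1.1) |
| 20% | 11.1% | 11.0% | 2.6% | 2.2 (1.1) |
| 30% | 26.4% | 26.3% | 7.4% | 2.3 (1.2) |
| 50% | 60.9% | 60.3% | 24.4% | 2.5 (1.3) |

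A simulation of 200,000 trials gave 2.2 to 2.5 extra patients over 10% to 50%. The small gap at 10% is sampling noise, since only about 726 of those trials had three early bleeds.

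**Worst case for the eight-patient condition.** Patients 1 to 3 are all experimental and all bleed; patients 4 to 8, five more, then enrol before the condition is met. This has probability 0.5³ × *p*³ = 0.125*p*³: 0.3% at 30% and 1.6% at 50%.

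**Balanced allocation.** With six experimental patients of 12, both preconditions are always met by the end, so they never change whether the rule fires. P(≥3 of 6) is 1.6% at 10%, 25.6% at 30% and 65.6% at 50%.

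**Section 4.1 beside Section 16.0.** Three bleeds correspond to 3/4 = 75% of four experimental patients or 3/6 = 50% of six. Neither matches a 30% criterion, and the printed directions are opposite. Section 16.0 also waits for eight patients, so it does not cover the earlier period.

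**The case against.** The strongest reply is that nobody is obliged to carry on. Investigators may stop whenever they choose, committees may review as needed and must approve continuation, and a serious bleed takes that patient off the randomised threshold, subject to the grade 3 exception. This stands. A reader might infer that the rule forces continued enrolment, or that early bleeds are lost. The documents support neither: discretion is unrestricted, and early events still count at patient 8. What is missing is a mandatory, pre-specified trigger. Discretion in an unblinded trial is not one, and a yearly review could fall after accrual has ended.

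A reader might also take larger sizes from the arithmetic than it supports:
- At a 50% rate, 24.4/60.9 = 40% of trials that reach three bleeds do so before patient 8. That is conditional on three bleeds, at a rate that no document figure supports.
- Eight months without a binding rule is not eight months of exposure. Three bleeds need three experimental patients, typically present only around patient 5 or 6.
- Under simple allocation there is a 36.3% chance that fewer than four of the first eight patients are experimental. This matters at patient 8 only if exactly three are experimental and all bleed: 56/256 × *p*³, or 0.6% at 30% and 2.7% at 50%. Balanced blocks that put four of the first eight patients on each arm would remove it.
- Bleeds may be recognised up to 30 days after randomisation (Section 7.7), so part of the delay would occur under any rule.

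Two further points stand. For a rate criterion such as Section 16.0's, a minimum number of patients does have a purpose, so the criticism applies to the Section 4.1 count. And stopping at patient 4 to 7 rather than 8 gives up some feasibility data, which is the trial's primary purpose.

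**Conclusion.** The concern holds in a limited form. The Section 4.1 preconditions buy almost nothing: over assumed rates from 10% to 50% they lower the chance of stopping by 0.01 to 0.7 percentage points under simple allocation, and by zero under balanced allocation. Their effect is to leave the period before the eighth enrolment without a mandatory stop.

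The practical size is modest. Three early bleeds are very unlikely at rates near the cited 3.8% and become a real possibility only if the lower threshold is much less safe, which is the case a safety rule is written for. The excess is then a little over two patients on average, half of them on the lower threshold. These figures rest on assumed bleeding rates, simple allocation and immediate knowledge of events. The conclusion that a count cannot fall rests on none of these. It is worth amending because the change is cheap and Section 16.0 has to be corrected in any case.

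**What to change.** In Section 4.1, keep the count of three experimental-arm patients, delete the enrolment and allocation preconditions, and state that the count is checked after each WHO grade 3/4 event in the experimental arm. Whether three is the right number is not questioned here.

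In the same amendment, reconcile Section 16.0 with Section 4.1. They differ in form (rate against count) and in printed direction, and both carry the eight-patient condition. Changing Section 4.1 alone would leave two conflicting statements; one trial-level stopping statement should remain.

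The cost is a short amendment. The chance of a false stop is essentially unchanged, and no power is lost because the study is descriptive. The downside is that a stop may come a few patients earlier, with slightly fewer feasibility data, in a trial that under the present wording would nearly always stop anyway.
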